5.7.1.5.1. Cohort 1 (primary objectives 1a,1b,1c and 1d)

To assess the 4 NI hypotheses related to Cohort 1 (CTP section 9.1), the neutralizing antibody response 14 days post Ad26.COV2.S booster vs the neutralizing antibody response 28 days post primary vaccination with Ad26.COV2.S will be used.

For the NI analysis, define the following groups:

- 1 = Ad26.COV2.S 5×10^{10} vp booster after Ad26.COV2.S (original virus)
- 2 = Ad26.COV2.S 5×10^{10} vp booster after Ad26.COV2.S (leading variant of high consequence or concern*), if feasible
- 3 = Ad26.COV2.S 2.5×10^{10} vp booster after Ad26.COV2.S (original virus)
- 4 = Ad26.COV2.S 1×10^{10} vp booster after Ad26.COV2.S (original virus)

R1 = Ad26.COV2.S 5×10^{10} vp primary vaccination (original strain) – (Reference group 1)

R2 = Ad26.COV2.S 5×10^{10} vp primary vaccination (leading variant of high consequence or concern*), if feasible (Reference group 2)

Success Criterion 1:

The responder rate induced in group k ($k = 1, 3, \text{ or } 4$) is NI as compared to the responder rate induced in group R1 using a NI margin of -10%. Similarly, the responder rate induced in group k ($k = 2$) is NI as compared to the responder rate induced in group R2, using a NI margin of -10%

Statistical method:

Objectives 1a and 1b (evaluated at the interim (if conducted) and primary analysis), 1c and 1d (evaluated only at the primary analysis).

To compute the differences in responder rates and associated Agresti-Min confidence intervals, let the dichotomous response post booster and post primary vaccination (reference) summary data be presented in a 2x2 table as follows.

Table 1: Paired Data Study Design Responses

		Post Booster		
Post Primary	Success	Failure	Total	
Success	a	b	a + b	
Failure	c	d	c + d	
Total	a + c	b + d	n	

Where,

- a = Number of participants responding favorably on both the post primary and on the booster
- b = Number of participants responding favorably on the post primary but unfavorably on the booster
- c = Number of participants responding unfavorably on the post primary but favorably on the booster
- d = Number of participants responding unfavorably on both the post primary and on the booster

Let $d = (\hat{P}_{Boost} - \hat{P}_{Primary})$ = Post booster responder rate – Post primary responder rate.

Then,

$$d = \frac{(a + c)}{n} - \frac{(a + b)}{n} = \frac{(c - b)}{n}$$

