Based on the data structure given in Table 1, the Agresti-Min (Agresti, A. & Min, Y. (2005).) point estimate and confidence interval (for the population responder difference rates, $\delta = (P_{Boost} - P_{Primary})$) lower and upper bounds are computed as follows:

$$\text{Lower limit} = \frac{(c^* - b^*)}{n^*} - Z_{\alpha/2} \sqrt{\left[(b^* + c^*) - \frac{(c^* - b^*)^2}{n^*} \right] / n^*}$$

$$\text{Upper limit} = \frac{(c^* - b^*)}{n^*} + Z_{\alpha/2} \sqrt{\left[(b^* + c^*) - \frac{(c^* - b^*)^2}{n^*} \right] / n^*}$$

Where $b^* = b + \frac{1}{2}$, $c^* = c + \frac{1}{2}$, and $n^* = n + 2$

For the NI assessment with respect to responder rates, in each group k (k = 1, 3, or 4) compared to the reference group R1 and in group k=2 compared to the reference group R2, the Agresti-Min (Agresti 2005) method, as described above, will be used to estimate the “within-participant” responder rate differences (i.e., booster vaccination after Ad26.COV2.S (original virus or leading variant of high consequence or concern*) minus primary vaccination (original strain or leading variant of high consequence or concern*) and its associated 2-sided $100 * (1 - 2 * \alpha)\%$ CI (where α = 1-sided significance level). This method was chosen because of its well-behaved Coverage Probability (CP) properties compared to other methods for the analysis of matched pairs data (Reed

2009). Coverage probability is generally used to evaluate $(1 - \alpha)$ CIs where α is the Type I error rate.

If an interim analysis is done (objectives 1a and 1b) with alpha spent = 0.0003 (1-sided) at the interim, based on the O'Brien-Fleming group sequential method assuming information fraction of 1/3, then the Agresti-Min method will result in the estimated responder rate difference and associated CI of 99.94% at the Interim analysis and 95.02% (for alpha=0.0249 (1-sided)) at the primary analysis, respectively. If at the time of the interim analysis, the assumption of 1/3 for information fraction is found not to be true, then the O'Brien-Fleming adjustments will be recalculated.

The estimated responder rate difference and associated 97.5% CI for Objectives 1c and 1d will be evaluated only at the primary analysis.

Remark: If no interim analysis is carried out, then the Agresti-Min method will result in the estimated responder rate difference and its 95% CI (objectives 1a and 1b) and 97.5% CI (objectives 1c and 1d) at the PA, respectively.

Success Criterion 2:

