Note: success criterion 2 will only be tested if success criterion 1 was met successfully for the hypothesis under consideration.

The GMT induced in group k ($k = 1, 3, \text{ or } 4$) is NI as compared to the GMT induced in group R1 using a NI margin of 2/3. Similarly, the GMT induced in group k ($k = 2$) is NI as compared to the GMT induced in group R2 using a NI margin of 2/3

Statistical method:

Objectives 1a and 1b (evaluated at the interim and primary analysis), 1c and 1d (evaluated only at the primary analysis)

The NI analysis on the GMR, in each group k ($k = 1, 3, \text{ or } 4$) compared to the reference group R1 and in group $k=2$ compared to the reference group R2 , will, respectively, use a paired t-test to estimate the within participant mean differences (i.e., booster vaccination after Ad26.COV2.S (original virus or leading variant of high consequence or concern*) minus primary vaccination (original strain or leading variant of high consequence or concern*) log10 transformed data, or equivalently change from primary on log10 transformed data) and its associated $100 * (1 - 2 * \alpha)\%$ CI (where $\alpha = 1$ -sided significance level). The estimated differences and its CIs will be back transformed to yield the GMR and its associated CI.

Similarly, if an interim analysis is done (objectives 1a and 1b) with alpha spent = 0.0003 (1-sided) at the interim, based on the O'Brien-Fleming group sequential method assuming information fraction of 1/3, then the back transformation of the log10 transformed data, will result in the

estimated GMR difference and associated 99.94% CI at the Interim analysis and 95.02% (for alpha=0.0249 (1-sided)) at the primary analysis, respectively. If at the time of the interim analysis, the assumption of 1/3 for information fraction is found not to be true, then the O'Brien-Fleming adjustments will be recalculated.

The estimated GMR difference and associated 97.5% CI for Objectives 1c and 1d will be evaluated only at the primary analysis.

Remark: If no interim analysis is carried out, then the estimated differences and its CIs will be back transformed to yield the GMR and its 95% CI (objectives 1a and 1b) and 97.5% CI (objectives 1c and 1d) at the PA, respectively.

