5.8.1. Interim Analysis

When at least 330 participants (see CTP Section **Error! Reference source not found.**) from Groups 1 to 3 in Cohort 1 have been enrolled and completed the Day 15 visit, it is estimated that immunogenicity data can be obtained from at least 110 participants in Group 1 to potentially

conduct an interim analysis. The planned primary non-inferiority testing of Cohort 1 – Group 1 may be performed on the available data from the Cohort 1 – Group 1 participants.

Scope of the Interim Analysis:

The interim analysis will consist of a statistical immunogenicity analysis of Cohort 1 – Group 1 participants only. Hypotheses 1a and 1b will be tested, in the hierarchical manner as outlined in **Error! Reference source not found.** (see CTP): Hypothesis 1b will only be tested if all success criteria of Hypothesis 1a are met. The other hypotheses (1c, 1d, 2a, 2b and 2c) will only be tested at the primary analysis.

In addition, limited safety/reactogenicity statistical outputs will be generated in a blinded manner, for all available participants (Cohort 1 and Cohort 2, all groups). The same outputs will be generated in an unblinded manner by the independent Statistical Support Group and will be shared only with the IDMC. The unblinded outputs may also be used to respond to questions or requests from Health Authorities. In this case, appropriate channels of communication will be used to keep the Sponsor blinded.

Alpha Spending:

An O'Brien-Fleming adjustment will be used whereby the type I error for the NI test at the interim analysis will be 0.0003 (one-sided). This alpha is calculated based on an estimated interim analysis sample size of 110 Cohort 1 – Group 1 participants (~33% of the total sample size). If immunogenicity data is available for more than 110 Cohort 1 – Group 1 participants at the time of the interim analysis, then the nominal alpha level of the interim analysis will be kept at 0.0003, but the alpha level at the primary analysis will be recalculated. The recalculation will be based on the O'Brien-Fleming adjustment and will take into consideration the alpha spent at the time of the interim analysis and the actual information fraction that was available at the time.

Procedures to maintain the study blind:

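### The printed Agresti-Min limits for Cohort 1 put the outer n* under the square root, which widens the interval by a factor of √n* and makes the −10% responder-rate criterion practically unattainable

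*SAP*

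**What the plan says.** Section 5.7.1.5.1 arranges the paired responses in a 2×2 table and defines the discordant cells as counts: "b = Number of participants responding favorably on the post primary but unfavorably on the booster" and "c = Number of participants responding unfavorably on the post primary but favorably on the booster". The effect is "Post booster responder rate – Post primary responder rate", which the section reduces to (c − b)/n.

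The section then says that the Agresti-Min "lower and upper bounds are computed as follows", and prints for both limits

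`(c*−b*)/n* ± Z_{α/2} · √{ [ (b*+c*) − (c*−b*)²/n* ] / n* }`, with `b* = b + ½`, `c* = c + ½`, `n* = n + 2`.

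The square brackets close before the last division by n*, and that division stands under the radical in both lines.

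The printed formula is the operative one: for the NI assessment "the Agresti-Min (Agresti 2005) method, as described above, will be used to estimate the" within-participant differences. Success Criterion 1 compares the booster responder rate with the "responder rate induced in group R1 using a NI margin of -10" per cent. Under Success Criterion 2, "success criterion 2 will only be tested if success criterion 1 was met successfully". Section 5.7.1.5 requires both co-primary endpoints, plus a GMR point estimate above 0.8, before NI is concluded.

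**The concern.** The starred quantities are counts, so the numerator under the radical estimates the variance of the count c − b. The variance of a count divided by n has n² in the denominator, or n outside the square root. The printed expression divides that variance by n* only once. It mixes two correct forms: the count form, with n* outside the radical, and the proportion form, with n* inside but with b*/n* and c*/n* in place of b* and c*.

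The formula decides a co-primary criterion for all four Cohort 1 objectives and controls whether the GMR criterion is tested. If it is coded as printed, a booster equal to or clearly better than primary vaccination would be reported as not having shown non-inferiority. If a library routine is used instead, the SAP and the program disagree on the primary analysis.

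**Working it through.** **Inputs**
- b, c (counts), the estimate (c − b)/n, `b*`, `c*`, `n*`, the printed limits and the −10% margin: SAP 5.7.1.5.1.
- CI levels: 95% for 1a/1b and 97.5% for 1c/1d without an interim; 99.94% (interim) and 95.02% (primary) for 1a/1b with one: SAP 5.7.1.5.1.
- Sample size: SAP 5.8.1 gives "an estimated interim analysis sample size of 110 Cohort 1" Group 1 participants, about 33% of the total, so n is about 330 at the primary analysis (inferred).
- Discordance rates: not given in the SAP. These are assumptions, taken over a range.

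**The plan's own figures.** A two-look O'Brien-Fleming boundary with overall one-sided 0.025 and information fraction 1/3 has constant 1.9625. It gives an interim p of 0.00034 (rounds to 0.0003) and a final p of 0.0249. Then 1 − 2×0.0003 = 99.94% and 1 − 2×0.0249 = 95.02%. The stated levels reproduce, so the problem lies in the limits alone.

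**Derivation.** Each pair contributes +1 (cell c), −1 (cell b) or 0. Hence
- estimated variance of (c − b) = (b + c) − (c − b)²/n
- estimated variance of (c − b)/n = [(b + c) − (c − b)²/n]/n²
- correct half-width = `Z·√[(b*+c*) − (c*−b*)²/n*] / n*`
- printed half-width = `Z·√{[(b*+c*) − (c*−b*)²/n*] / n*}`
- ratio printed/correct = n*/√n* = √n*: √332 = 18.2 at n = 330, √112 = 10.6 at n = 110.

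**Worked cases, n = 330, n* = 332, Z = 1.96**
- b = c = 0: `b*+c*` = 1, difference 0. Printed 1.96×√(1/332) = 10.8%; correct 1.96/332 = 0.6%. Perfect agreement in all 330 pairs gives a printed lower limit of −10.8%, which fails.
- b = c = 10: `b*+c*` = 21. Printed 1.96×√(21/332) = 49.3%; correct 1.96×√21/332 = 2.7%.
- b = 10, c = 100: centre 90/332 = 27.1%; bracket 111 − 8100/332 = 86.6. Printed half-width 1.96×√(86.6/332) = 100.1%, giving −73% to +127%. Correct half-width 1.96×√86.6/332 = 5.5%, giving +21.6% to +32.6%. A difference of proportions cannot exceed 100%.

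**Interim, n = 110, 99.94% CI, b = c = 0:** printed lower limit −32.4%, correct −3.1%.

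**What it would take to pass as printed**

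| Setting | Condition for the printed limit to exceed −10% |
|---|---|
| No discordant pairs, 95% CI | n ≥ 383 |
| No discordant pairs, 97.5% CI | n ≥ 501 |
| n = 330, b = 0, 95% CI | c ≥ 250 (booster about 76 points better) |
| n = 330, b = 0, 97.5% CI | c ≥ 267 (about 81 points) |
| n = 110, b = 0, 99.94% CI | c ≥ 103 (about 94 points) |

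**Simulation** (multinomial, 200,000 replicates, n = 330, 95% CI)

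| True b / c rates | Pass rate, printed | Pass rate, corrected |
|---|---|---|
| 5% / 5% | 0 | 99.99% |
| 10% / 10% | 0 | 98.2% |
| 15% / 15% | 0 | 91.4% |
| 5% / 30% | 0 | 100% |
| 2% / 50% | 0 | 100% |
| 2% / 70% | 0.04% | 100% |

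In these scenarios the printed interval covered the true difference in every replicate. The corrected one covered it in about 95%.

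**The case against.** - **Rendering.** The defect turns on how far a radical bar extends, so a typesetting or conversion slip is possible and the source page should be checked. But both limits show the same form, and the square brackets under the radical are needed only if the division by n* is under it too.
- **The method is named and cited.** A validated Agresti-Min routine may well give correct limits, and the SAP justifies its choice by good coverage, which the printed formula does not have. This lowers the chance that the error reaches the results. It does not cure the text, because the SAP points to the method as it is described there, and section 5.7.1.5.2 names SAS but no routine for these limits.
- **The output would look absurd.** An upper limit of +127% should be noticed. With few discordant pairs, though, a lower limit such as −10.8% looks plausible and simply fails.
- **Direction.** The error is conservative. It cannot create a false non-inferiority claim, and the sensitivity analysis in 5.7.1.5.3 would probably expose the discrepancy for 1a, 1c and 1d. That analysis does not replace the primary test and omits 1b.
- **Not strictly impossible.** A booster advantage of about 76 points or more could pass. This stands, and is why the criterion is called practically rather than absolutely unattainable.

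**Conclusion.** The concern holds. As printed, both limits overstate the standard error by exactly √n*. That factor follows from the SAP's own definitions and rests on no assumed rate or outside source. At about 330 pairs, Success Criterion 1 fails even with complete agreement between the two time points, and it passes only if the booster responder rate exceeds the primary rate by roughly 76 points (95% CI, b = 0).

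The numerical examples assume n = 330, inferred for Group 1 from section 5.8.1 and carried over to the other dose groups for 1c and 1d. The pass rates also assume the discordance rates shown. How a failure spreads through the testing hierarchy depends on the protocol's decision tree (CTP section 9.1), which was not available. The gate between the two success criteria within each hypothesis is in the SAP itself. The actual harm depends on whether the formula is programmed as printed. Because it specifies a co-primary criterion, it must be corrected.

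**What to change.** Replace both limits in section 5.7.1.5.1 by

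`(c*−b*)/n* ± Z · √[ (b*+c*) − (c*−b*)²/n* ] / n*`

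Only the outer n* moves; the n* beneath (c*−b*)² stays where it is. Add one worked example to the DPS as a program check, for instance n = 330, b = 10, c = 100, 95% CI, result +21.6% to +32.6%.

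In the same edit, align the quantile. The formula prints Z_{α/2}, while the section defines α as one-sided with a 100(1−2α)% interval. Taken literally, α = 0.025 would give a 97.5% interval, not 95%. This is a separate matter of notation.

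The cost is a correction to two printed lines and one example in the DPS. No data, design or analysis-set change is needed.

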5.7.1.5.2. Cohort 2 (primary objectives 2a,2b 2c, and 2d)

Serum samples of approximately 300 individuals collected 2 weeks to 2 months after completion of the 2-dose primary vaccination with Pfizer BNT162b2 obtained from external sources will be used to assess NI of the neutralizing antibody response 14 days post Ad26.COV2.S booster vs the neutralizing antibody response 2 weeks to 2 months after completion of the 2-dose primary vaccination with Pfizer BNT162b2 in the 4 hypotheses related to Cohort 2 (CTP section 9.1).

For the NI analysis, define the following groups:

5 = Ad26.COV2.S 5×10^{10} vp booster vaccination after Pfizer (original virus)

6 = Ad26.COV2.S 5×10^{10} vp booster vaccination after Pfizer (leading variant of high consequence or concern*), if feasible

7 = Ad26.COV2.S 2.5×10^{10} vp booster vaccination after Pfizer (original virus)

8 = Ad26.COV2.S 1×10^{10} vp booster vaccination after Pfizer (original virus)

R3 = 2-dose Pfizer BNT162b2 primary vaccination (original strain) (referred to as Pfizer BNT162b2 external samples) (Reference group 3)

R4 = 2-dose Pfizer BNT162b2 primary vaccination (leading variant of high consequence or concern*), if feasible (referred to as Pfizer BNT162b2 external samples) (Reference group 4)

Success Criterion 1:

The Seropositivity rate induced in group k (k = 5, 7, or 8) is NI as compared to the Seropositivity rate induced in group R3, using a NI margin of -10%. Similarly, the Seropositivity rate induced in group k (k = 6) is NI as compared to the Seropositivity rate induced in group R4, using a NI margin of -10%

Statistical method:

The $100 * (1 - 2 * \alpha)\%$ CI (where α = 1-sided significance level) for differences in Seropositivity rate between each group 5, 7, 8 and R3 (Reference group 3) and between group 6 and R4 (Reference group 4) will, respectively, be computed using the Farrington & Manning Likelihood Score Test method.

The rate will be converted to percentage and if the lower limit of the CI is > -10 , then it will be concluded that success criterion 1 for the given hypothesis has been met. In that case, success criterion 2 will be tested for the hypothesis under consideration. Otherwise, the testing will be ended, and it will be concluded that NI has not been demonstrated for the hypothesis under consideration.

Success Criterion 2:

Note: success criterion 2 will only be tested if success criterion 1 was met successfully for the hypothesis under consideration.

The GMT induced in group k ($k = 5, 7$, or 8) is NI as compared to the GMT induced in group R3 using a NI margin of $2/3$. Similarly, the GMT induced in group k ($k = 6$) is NI as compared to the GMT induced in group R4 using a NI margin of $2/3$

Statistical method:

Objectives 2a, 2b, 2c and 2d: evaluated only at the primary analysis

The NI analysis on the GMR, in each group g ($g = 5, 7$, or 8) compared to the reference group R3 and in group $k=6$ compared to the reference group R4, will, respectively, be assessed by first constructing the 2-sided $(1 - 2*\alpha)$ % confidence interval for the difference in means (i.e., booster vaccination after Ad26.COV2.S (original virus or leading variant of high consequence or concern*) minus primary vaccination (original strain or leading variant of high consequence or concern*) log10 transformed data) based on the sampling distribution of two independent normal distributions with variances that are unknown but assumed equal.

Let $X_g = \log_{10} Y_g \sim N(\mu_g, \sigma_g)$, normally distributed with true population mean and standard deviation, μ_g and σ_g respectively and where X_g is the log-transformed (log₁₀ scale) virus neutralization assay (VNA) titers for Cohort 2 booster vaccine groups, $g = 5, 6, 7, 8$ (so defined to reflect the hypotheses in Figure 3 Refer to Clinical Trial Protocol (CTP); section 9.1).

Let $X_R = \log_{10} Y_R \sim N(\mu_R, \sigma_R)$, where X_R ($R = R_3$ or R_4) is the log-transformed (log₁₀ scale) virus neutralization assay (VNA) titers for the 2-dose Pfizer BNT162b2 primary vaccination (original strain) (Reference group 3) or the 2-dose Pfizer BNT162b2 primary vaccination (leading variant of high consequence or concern*), if feasible (Reference group 4)

It can be shown that the log-transformed (log₁₀ scale) virus neutralization assay (VNA) titers mean differences between the vaccine groups g , $(\bar{X}_g - \bar{X}_R)$, is equal to the log-transformed (log₁₀ scale) ratio of the corresponding geometric means, i.e., $\log_{10}(GMT_g/GMT_R)$

Hence, back transforming yields, $GMT_g/GMT_R = 10^{(\bar{X}_g - \bar{X}_R)}$ as the geometric mean ratio estimates.

Next, we can construct the $(1 - 2*\alpha)\%$ confidence interval (2-sided) (where $\alpha = 1$ -sided significance level), for the geometric mean ratios, by first constructing the confidence interval on the difference on the means, $(\bar{X}_g - \bar{X}_R)$.

Assuming unknown equal variances for the population cohort 2 booster vaccine groups g and the reference group, R, and log-transformed (log₁₀ scale) virus neutralization assay (VNA) titers, the (1 - 2* α) % confidence interval (2-sided), (where α = 1-sided significance level), estimate for the population mean differences, is given by,

$$(\overline{X_g} - \overline{X_R}) \pm t_{(1-2*\alpha/2; v_p)} S_p \sqrt{\left(\frac{1}{n_g} + \frac{1}{n_R}\right)}$$

Where the *pooled variance estimate*, $S_p^2 = \frac{(n_g-1)S_g^2 + (n_R-1)S_R^2}{n_g+n_R-2}$ and $v_p = n_g + n_R - 2$ is the degrees of freedom for the t-distribution and $\alpha = 0.025$.

Since log transformation is monotone, back transforming confidence intervals for the difference in means in the log10 scale gives a confidence interval for the ratio of the geometric means. Hence, the lower and upper bounds of the 2-sided (1 - 2 * α)% (i.e., 97.5% since $\alpha = 0.0125$ (1-sided)) confidence interval for the GMT ratios are as follows:

$$((GMT\ Ratio))_{Lower\ Limit} = 10^{\left((\overline{X_g} - \overline{X_R}) - t_{(1-\alpha/2; v_p)} S_p \sqrt{\left(\frac{1}{n_g} + \frac{1}{n_R}\right)} \right)}$$

$$((GMT\ Ratio))_{Upper\ Limit} = 10^{\left((\overline{X_g} - \overline{X_R}) + t_{(1-\alpha/2; v_p)} S_p \sqrt{\left(\frac{1}{n_g} + \frac{1}{n_R}\right)} \right)}$$

If the assumptions of the unknown equal variances for the independent normal distributions of cohort 2 booster vaccine groups g and the reference group, R, do not hold (i.e., test of equality variances shows that the variances are significantly different), then an approximate t-distribution with Satterthwaite approximated degrees of freedom will be used instead (Casella, G & Berger L.R (1990)).

For each of the booster vaccine groups, g comparisons, NI will be demonstrated if

$((GMR\ Ratio))_{Lower\ Limit} > \frac{2}{3}$, where the lower limit corresponds to a 97.5% 2-sided confidence interval.

SAS v 9.4 will be used in implementing the NI comparisons.

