5.7.1.5. NI Analysis – Success Criterion and Statistical method

Formal NI testing in Cohort 1 will be conducted as a “within-participants” analysis, in which participants’ VNA data are considered matched pairs across the two time points. However, the formal NI testing in Cohort 2 will be conducted as between participant analysis comparing COV2008 Pfizer cohort (cohort 2) vs. the external Pfizer samples VNA data.

For each Primary objective in Cohort 1 and Cohort 2, the NI tests will be performed on the NI analysis set and must be demonstrated on both co-primary endpoints as well as on the GMR estimate criterion to conclude NI:

- GMR
- Responder rate for Cohort 1 and seropositivity rate for cohort 2
- An estimated GMR (GMT Day 15 post-booster/GMT post primary regimen) of >0.8

The primary responder definition (FDA) (see section 5.7.1.6.2.1) will be used for the NI assessment of the primary objectives.

Furthermore, hierarchical testing will be applied to the NI hypotheses in the cohorts (see CTP section 9.1; Figure 3: Decision Tree-based Hypothesis Testing).

In addition to the hierarchical NI hypotheses testing results, forest plot of responder rate (cohort 1) and seropositivity rate (cohort 2) differences and GMRs associated with the NI Hypotheses will be presented by cohort. The forest plots will also be presented by age group (see section 5.7.2).

The success criterion and the corresponding statistical methods to be used are as described below for each cohort.

Remark: Note that, in general, the lower bound of a 2-sided $100 * (1 - 2 * \alpha)\%$ CI (where $\alpha = 1$ -sided significance level) is equivalent to the lower bound of the 1-sided $100 * (1 - \alpha)\%$ CI which is needed for the NI hypothesis testing.

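### Neither printed formula for the Cohort 2 GMR interval, with the alpha stated beside it, gives the 97.5% CI that the non-inferiority rule requires

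*SAP*

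**What the plan says.** SAP Section 5.7.1.5.2, Success Criterion 2, sets out the GMR test for Cohort 2. Alpha is the one-sided significance level, and the interval is two-sided with coverage 1 − 2α.

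The SAP describes one interval on two scales. The GMR interval is obtained "for the geometric mean ratios, by first constructing the confidence interval on the difference on the means", and the section adds that "back transforming confidence intervals for the difference in means in the log10 scale gives a confidence interval for the ratio of the geometric means".

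Three statements then fix the level:

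- **Log10 difference.** The multiplier is t at probability 1 − 2α/2, and the line below the formula says that v_p "is the degrees of freedom for the t-distribution and $\alpha = 0.025".
- **Back-transformed GMT ratio limits.** The introducing sentence gives the level as "97.5% since $\alpha = 0.0125$ (1-sided"), but the multiplier printed in both limits is t at probability 1 − α/2.
- **Decision rule.** The lower limit must exceed 2/3, "where the lower limit corresponds to a 97.5% 2-sided confidence interval".

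**The concern.** Both formulas describe the same interval, so they must use the same t quantile. They differ in the subscript and in the alpha stated beside it, and neither combination matches the level in the decision rule.

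These limits settle one of the criteria that hypotheses 2a to 2d must all meet. A programmer who codes the ratio limits as printed would apply a stricter test than planned. One who computes the log10 interval with its own stated alpha and back-transforms it would apply a more liberal test. Near the margin, the same data could pass or fail depending on which line was coded.

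**Working it through.** **Inputs from SAP Section 5.7.1.5.2:** alpha one-sided with coverage 1 − 2α; the two t subscripts; the two alpha values (0.025 and 0.0125); the 97.5% level in the decision rule; the margin of 2/3; and the external group ("Serum samples of approximately 300 individuals collected 2 weeks to 2 months after completion"). Section 5.7.1.5 adds a further criterion: "An estimated GMR (GMT Day 15 post-booster/GMT post primary regimen) of >0.8".

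**Step 1: the level required.** A two-sided interval built on the t quantile at probability q has coverage 2q − 1 and one-sided error 1 − q. For 97.5%, q = (1 + 0.975)/2 = 0.9875 and the one-sided error is 0.0125. Under the SAP's definition this is q = 1 − α with α = 0.0125.

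**Step 2: what each formula gives with each printed alpha.**

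| Subscript | α | q | Two-sided CI | One-sided error |
|---|---|---|---|---|
| 1 − 2α/2 (log10 difference) | 0.025, stated beside it | 0.975 | 95% | 0.025 |
| 1 − α/2 (ratio limits) | 0.0125, stated beside it | 0.99375 | 98.75% | 0.00625 |
| 1 − 2α/2 | 0.0125, crossed | 0.9875 | 97.5% | 0.0125 |
| 1 − α/2 | 0.025, crossed | 0.9875 | 97.5% | 0.0125 |

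The stated 97.5% is reproduced only when a formula is paired with the other formula's alpha.

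**Step 3: could the two alphas belong to different analyses?** An interim split does not explain them: "Objectives 2a, 2b, 2c and 2d: evaluated only at the primary analysis". A split by objective does not either, because the decision rule applies 97.5% to every booster group comparison in Cohort 2.

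**Step 4: size.** The section gives no SD or booster group size. Assumed ranges: booster group 200 to 330, log10 SD 0.4 to 0.6, true GMR 0.85 to 1.2. The external group is taken as 300.

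With 300 per group there are 598 degrees of freedom, and the t quantiles are 1.9639 (95%), 2.2471 (97.5%) and 2.5053 (98.75%).

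Smallest passing GMR = max(0.8, (2/3) × 10^(t × SD × √(1/n + 1/300))).

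For n = 300 and SD 0.5, the standard error is 0.5 × √(2/300) = 0.0408, so:

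- 95%: (2/3) × 10^(1.9639 × 0.0408) = 0.802
- 97.5%: (2/3) × 10^(2.2471 × 0.0408) = 0.823
- 98.75%: (2/3) × 10^(2.5053 × 0.0408) = 0.844

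Before the 0.8 floor, SD 0.4 gives 0.773, 0.789 and 0.805, and SD 0.6 gives 0.832, 0.859 and 0.884.

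The next table gives the probability of meeting both GMR criteria with 300 per group, integrating over the distribution of the pooled SD. Entries are for the 95%, 97.5% and 98.75% intervals in that order.

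| True GMR | SD 0.4 | SD 0.5 | SD 0.6 |
|---|---|---|---|
| 2/3 (error) | 0.008, 0.008, 0.006 | 0.024, 0.0125, 0.006 | 0.025, 0.0125, 0.006 |
| 0.85 | 0.79, 0.79, 0.76 | 0.73, 0.63, 0.53 | 0.58, 0.46, 0.36 |
| 0.90 | 0.94, 0.94, 0.93 | 0.89, 0.83, 0.75 | 0.76, 0.66, 0.56 |
| 1.0 | 0.998 for all three | 0.99, 0.98, 0.96 | 0.95, 0.91, 0.86 |

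At a true GMR of 1.2 the lowest value is 0.9965 (SD 0.6, 98.75% CI). For SD 0.5 and a true GMR of 0.85, a booster group of 200 gives 0.636, 0.526 and 0.423, and one of 330 gives 0.741, 0.655 and 0.556. A simulation of 400,000 trials (300 per group, SD 0.5) agreed to within 0.001. The seropositivity criterion, which must be passed first, is not modelled and can only lower these figures.

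**The case against.** The strongest reply is that this is a slip of notation. The 97.5% level appears both in the sentence introducing the ratio limits and in the decision rule. A programmer who follows the stated level gets the right interval. The crossed pairings support this reading: 0.025 looks like a total two-sided alpha that has strayed into a section where alpha is one-sided. The ratio limits as printed are also conservative, so read literally they do not inflate the type I error. The liberal case arises only if someone sets those limits aside and back-transforms the log10 interval with α = 0.025.

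These points stand and limit the seriousness. They do not remove the error, because the crossed pairings contradict the alpha printed with each formula and the SAP calls alpha one-sided throughout this derivation.

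A second reply is that 0.025 was carried over from Cohort 1. There, 95% intervals (objectives 1a and 1b) and 97.5% intervals (1c and 1d) coexist even without an interim analysis (Section 5.7.1.5.1). That may be how the value arose, but it is another cohort's scheme. The Cohort 2 decision rule has one level for all comparisons.

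A third reply is that the power differences rest on an assumed SD and group size and matter only in part of the range. That is correct.

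**Conclusion.** The inconsistency is real and follows from the printed text alone. With the alphas beside them, the two formulas give 95% and 98.75% intervals where the rule requires 97.5%. Literal use of the ratio limits halves the one-sided level, from 0.0125 to 0.00625. Literal use of the log10 formula doubles it to 0.025.

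The practical effect depends on assumptions the SAP does not supply. It is material when the true GMR is about 0.85 to 0.90 with a log10 SD of 0.5 or more. At a GMR of 0.85 and SD 0.5, going from the intended to the printed decision limits costs 0.63 − 0.53 = 0.10 in power. It is small at SD 0.4, where the 0.8 criterion largely takes over, and negligible at a true GMR of 1.2. If the stated 97.5% is followed, nothing changes. It should be corrected because a confirmatory decision limit ought to have one reproducible formula, but it does not call the design or the chosen level into question.

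**What to change.** In SAP Section 5.7.1.5.2, Success Criterion 2:

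- delete α = 0.025 from the line under the log10-difference formula;
- state α = 0.0125 (one-sided) once, before the first formula;
- use t(1 − α; v_p) in the log10-difference formula and in both back-transformed limits.

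All three expressions then use the 0.9875 quantile and give the 97.5% two-sided interval of the decision rule. The cost is a text correction. Data, design, margin and the stated level do not change.
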